#### **7.1.5 UNEXPECTED ADVERSE DRUG REACTIONS AND EXPEDITED REPORTING**

An adverse drug reaction (ADR) is any noxious and unintended responses to a medicinal product related to any dose, for which a causal relationship between a medicinal product and an adverse event is at least a reasonable possibility (i.e., there is evidence to suggest a causal relationship between the product and the adverse event). An unexpected ADR is one, the nature or severity of which is not consistent with the applicable product information (Investigator's brochure, protocol, and user manual). Reports that add significant information on specificity or severity of a known, already documented SAE constitute unexpected events. For example, an event more specific or more severe than described in the Investigator's Brochure or protocol would be considered "unexpected". Specific examples would be (a) acute renal failure as a labeled ADR with a subsequent new report of interstitial nephritis and (b) hepatitis with a first report of fulminant hepatitis.

The Sponsor will assess each serious ADR report for expectedness, to determine if it is a serious unexpected suspected adverse reaction (SUSAR) which requires prompt reporting to regulatory authorities and participating Investigators as an expedited report, according to the applicable regulatory requirements. Additional occurrences of the SUSAR will be required to be reported on an expedited basis until the applicable product information is amended.

In addition to single-case reports of SUSARs, the Sponsor shall notify regulatory authorities and participating Investigators of information that might materially influence the benefit-risk assessment of a medicinal product, sufficient to consider changes in product administration or overall conduct of a clinical investigation. Examples of such information include a clinically important increase in the rate of occurrence of a serious

expected adverse event, the identification of a significant hazard to the subject population, or a major safety finding from a study conducted in animals.

#### **7.1.6 UNANTICIPATED (SERIOUS) ADVERSE DEVICE EFFECT (UADE)**

Unanticipated adverse device effect means any serious adverse effect on health or safety or any life-threatening problem or death caused by, or associated with, a device, if that effect, problem, or death was not previously identified in nature, severity, or degree of incidence in the investigational plan or application (including a supplementary plan or application), or any other unanticipated serious problem associated with a device that relates to the rights, safety, or welfare of subjects.

Per the definition above, a UADE is a type of serious adverse event (SAE) that requires expedited reporting on the part of the sponsor. As a reminder, all SAEs regardless of relationship to device, drug or procedure are to be reported to Sponsor by the study Investigator within 24 hours. Sponsor will assess each device related SAE to determine if anticipated based on prior identification within the investigational plan.

#### **7.1.7 ASSESSING SEVERITY (INTENSITY)**

Adverse events should be captured once on the CRF at the maximum severity reported. The Investigator will grade laboratory AEs and clinical AEs with respect to the following levels of severity as per Common Toxicity Criteria for Adverse Events (CTCAE) v 4.03 for applicable subject populations:

- Mild (Grade 1)
- Moderate (Grade 2)
- Severe (Grade 3)
- Potentially Life Threatening (Grade 4)
- Death (Grade 5)

The Investigator will grade injection site reactions in accordance with September 2007 FDA Guidance for Industry—Toxicity Grading Scale for Healthy Adult and Adolescent Volunteers Enrolled in Preventive Vaccine Clinical Trials.

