## 7. EVALUATION OF SAFETY AND MANAGEMENT OF TOXICITY

### 7.1 SAFETY PARAMETERS

#### 7.1.1 ADVERSE EVENTS

An adverse event (AE) is defined as any unfavorable and unintended change in the structure, function, or chemistry of the body, or worsening of a pre-existing condition, temporally associated with the use of a product whether or not considered related to the use of the product. In this study, such changes will be monitored, classified, and summarized, as Clinical or Laboratory AEs. Medical condition/diseases present before starting the investigational drug will be considered adverse events only if they worsen after starting study treatment. Throughout the course of the study, all solicited and unsolicited AEs will be monitored and reported on an AE CRF, including the event's seriousness, severity, action taken, and relationship to investigational product(s). AEs should be followed until resolution or stable and the outcome will be documented on the appropriate CRF. All AEs should be recorded in standard medical terminology rather than the subject's own words.

AEs include the following:

- Pre- or post-treatment complications that occur as a result of protocol mandated procedure during or after screening (before the administration of study drug).
- Any pre-existing condition that increases in severity, or changes in nature during or as a consequence of the study drug phase of a human clinical trial, will also be considered an AE.
- Complications of pregnancy (e.g., spontaneous abortion, miscarriage, ectopic pregnancy, fetal demise, still birth, congenital anomaly of fetus/newborn); see [Section 7.1.11](#) for additional information.
- AEs that occur from the study screening visit onwards and throughout the duration of the study, including the follow-up off study drug period will be recorded as an AE.
- Conditions that lead to a medical or surgical procedure.

AEs do not include the following:

- Medical or surgical procedures (e.g., surgery, endoscopy, tooth extraction, transfusion) performed as a result of an AE.
- Pre-existing diseases or conditions or laboratory abnormalities present or detected before the screening visit that **do not worsen**.
- Situations where an untoward medical occurrence has not occurred (e.g., hospitalization for elective surgery, social and/or convenience admissions).
- Overdose without clinical sequelae.

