## **8.11 SAFETY ANALYSES**

### **8.11.1 ADVERSE EVENTS**

All AEs will be summarized among the safety population by frequency per treatment arm. These frequencies will be presented overall and separately by dose, and will depict overall, by system organ class and by preferred term, the percentage of subjects affected. Additional frequencies will be presented with respect to maximum severity and to strongest relationship to Study Treatment. Multiple occurrences of the same AE will be counted only once following a worst-case approach with respect to severity and relationship to Study Treatment. All serious AEs will also be summarized as above.

The main summary of safety data will be based on events occurring within 14 days of any dose. For this summary, the frequency of preferred term events will be summarized with percentages and exact Clopper-Pearson 95% confidence intervals. Separate summaries will be based on events occurring within 7 days of any dose and regardless of when they occurred.

Any AEs with a missing or partial onset date will be included in the overall AEs, but not be included within specified day-range summaries. AE duration will be calculated as (Stop Date – Start Date) + 1.

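### With one record per adverse event at its worst grade, an event that stays open across a later VGX-3100 dose and then worsens can drop out of the 7- and 14-day summaries or sit under the earlier dose

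*Protocol*

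**What the plan says.** Section 7.1.7 sets the recording rule for sites: "Adverse events should be captured once on the CRF at the maximum severity reported".

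Section 8.11.1 sets the tables:
- By dose: "These frequencies will be presented overall and separately by dose, and will depict overall, by system organ class and by preferred term", as the percentage of subjects affected.
- By grade: "Additional frequencies will be presented with respect to maximum severity and to strongest relationship to Study Treatment". These are not said to be split by dose or by time window.
- Main summary: "The main summary of safety data will be based on events occurring within 14 days of any dose". Its content is described as follows: "For this summary, the frequency of preferred term events will be summarized with percentages and exact Clopper-Pearson 95% confidence intervals".
- Further summaries are to "be based on events occurring within 7 days of any dose and regardless of when they" occurred.
- Date rule: "Any AEs with a missing or partial onset date will be included in the overall AEs, but not be included within specified day-range summaries".

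The same section counts repeat occurrences of an event once, at the worst severity and relationship, and computes duration from a single start and a single stop date.

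Section 7.1.1 lists among the things that are adverse events: "Any pre-existing condition that increases in severity, or changes in nature during or as a consequence of the study drug phase". Section 7.2 collects adverse events from informed consent to Week 100.

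Sections 7 and 8 are visible up to Version 2.0. The Version 2.1 list of changes names no edit to 7.1.7 or 8.11.1.

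**The concern.** A table restricted to the days after dosing is meant to show what happens soon after a dose, including an ongoing reaction that gets worse on re-dosing. Section 7.1.8 itself asks investigators to weigh timing and reintroduction of the product when judging causality. If each event has one line, one onset date and its eventual worst grade, the date of worsening is not in the adverse-event data, and no later analysis document can recover it. That makes this a data-collection matter and not something left to the SAP.

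The events most exposed are long-lasting ones. In the combination arm, imiquimod is applied from Day 0 through Week 20, which spans the first three VGX-3100 doses, and Section 1.1.16 names local skin and application-site reactions as its most frequent adverse reactions.

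A related gap concerns events first recorded between consent and Day 0. Under 7.1.7 such an event is one record with a pre-dose onset. Section 7.1.1 treats the worsening of a pre-existing condition as an adverse event. The two sections do not say together whether the later worsening gets its own entry.

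**Working it through.** The protocol gives no figure for this point, so there is none to reproduce. The check places illustrative events against the dose schedule.

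**Inputs**
- Dose days: 0, 28, 84 and 168 (Day 0, Weeks 4, 12 and 24; synopsis dosing schedule).
- Windows: 7 and 14 days after any dose (8.11.1), counted here as days 0 to 7 and 0 to 14 after each dose.
- Placing date: onset, as implied by the missing-date rule in 8.11.1.
- Onset and worsening days below are assumptions chosen to show the mechanism.

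**Placing by onset and by worsening date**

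| Onset | Worsens | 14-day window by onset | 7-day window by onset | Both windows by worsening date |
|---|---|---|---|---|
| Day 10 | Day 30 | dose 1 | none | dose 2 |
| Day 20 | Day 30 | none | none | dose 2 |
| Day 60 | Day 86 | none | none | dose 3 |
| Day 90 | Day 170 | dose 3 | dose 3 | dose 4 |

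Rows 2 and 3 are missing from both window summaries, although the worsening came two days after a dose. Row 1 is missing from the 7-day summary only. Rows 1 and 4 belong to the earlier dose in a by-dose table. The window summaries pool all doses, so row 4 is counted in them either way.

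**Window coverage before dose 4**
- 14-day windows: 3 doses × 15 days = 45 days; 45/168 = 26.8%.
- 7-day windows: 3 × 8 = 24 days; 24/168 = 14.3%.
- Over the 140 days of imiquimod: 45/140 = 32.1% and 24/140 = 17.1%.

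**How long an event must last to be affected.** It must be open at a later dose. Scheduled gaps between doses are 28, 56 and 84 days. With the ±7-day visit windows (Day 0 fixed), the shortest gaps are 28 − 7 = 21, 56 − 14 = 42 and 84 − 14 = 70 days. An event that begins late in a gap needs to last less than the whole gap.

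**The case against.** Recording each event once at its worst grade is an ordinary convention. Section 7.1.7 does not say in words that a worsened event keeps its first onset date, and CRF completion guidelines or a SAP, neither shown, could deal with dating. Injection-site reactions are described as generally mild and lasting a few days at most, so few will span a dosing visit. A reaction that resolves and returns after the next dose is a new occurrence with its own onset, and the diary covers 7 days after each dose. Because the tables count subjects by preferred term, a subject with any other in-window onset of the same term is already in the 14-day summary. Nothing vanishes from safety reporting: the event stays in the all-time and overall maximum-severity summaries, and the stopping rules, AESI and SAE reporting do not depend on these tables.

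Most of this stands and limits the extent. It does not remove the mechanism. Keeping the first onset date is an inference, but it follows from one record with one start date. CRF guidance that split the record would depart from the instruction to capture the event once.

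Three stronger readings are tempting but unsupported:
- A reader might infer that the 14-day and 7-day summaries credit a worst grade to the wrong dose. They pool all doses, and the 14-day summary is described as preferred-term frequencies without grade. Their error can only be omission.
- A reader might infer that 73% of events (the complement of 27%) are lost. That would need onset spread evenly over time, and it ignores that an event must also persist across a later dose and worsen.
- A reader might infer that worsening of a condition present before Day 0 is simply ignored. Section 7.1.1 already makes it an adverse event; what is missing is its reconciliation with 7.1.7.

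**Conclusion.** The point holds in a narrow form. For an adverse event that remains open across a later VGX-3100 dose and then worsens, the rules in 7.1.7 and 8.11.1 together give one of two results: omission from the 7- or 14-day summary if onset fell outside that window, or placing under the earlier dose in the by-dose tables. A worst grade would be shown under the wrong dose only if the maximum-severity tables were also split by dose, which the protocol does not state.

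The number of events affected cannot be derived from the documents. The 27% describes the calendar only. The conclusion assumes that onset date is the placing date, which 8.11.1 implies without stating, that an open event is not split on the CRF, and that Version 2.1 left both sections as they are. Primary efficacy is untouched. This is an inexpensive improvement to descriptive safety tables that is best made while data are still being collected.

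**What to change.** Amend 7.1.7 in one of two ways. When an ongoing event rises in grade after a subsequent VGX-3100 dose, or after Day 0 if it was present before, either enter a new record at the higher grade dated from the worsening, or keep one record and collect the date of each grade increase. State that the Day 0 case is how 7.1.1 and 7.1.7 are reconciled.

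In 8.11.1, say that this date places the event in the by-dose and day-range tables. Keep the rule that a subject is counted once at worst grade; it already prevents double counting within a preferred term. If records are split, link them so that the duration formula can still give the length of the whole event.

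Cost: a CRF completion instruction, a sentence in each of the two sections, and a few more adverse-event lines to enter.

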#### **7.1.8 CASUAL RELATIONSHIP OF CLINICAL MATERIAL TO ADVERSE EVENTS**

A causally related AE is one judged to have a reasonable possibility of a relationship to the administration of the IP and/or the investigational device. An AE may also be assessed as not related to the IP and/or the investigational device. Because the Investigator is knowledgeable about the subject (e.g., medical history, concomitant medications), administers the IP, and monitors the subject's response to the IP, the Investigator is responsible for reporting adverse events and judging the relationship between the administration of the IP and device and a subsequent AE. The Investigator is aware of the subject's clinical state and thus may be sensitive to distinctions between events due to the underlying disease process versus events that may be product related and may have observed the event. The Sponsor will assess the overall safety of the IP delivered by EP and determine whether to report expeditiously to the regulatory agencies.

Investigators should use their knowledge of the subject, the circumstances surrounding the event, available site and non-site laboratory and clinical records, and an evaluation of any potential alternative causes to determine whether or not an adverse event is considered to be related to the IP and/or the investigational device indicating "yes" or "no" accordingly. Causality should be assessed by the Investigator as "yes, related" or "no, unrelated" by the following criteria:

- Yes – there is a reasonable possibility that administration of the Study Treatment contributed to the event;
- No – there is no reasonable possibility that administration of the Study Treatment contributed to the event and there are more likely causes.

The following guidance should also be taken into consideration:

- Temporal relationship of event to administration of IP and/or the investigational device;
- Course of the event, considering especially the effects of dose reduction, discontinuation of IP, or reintroduction of IP (where applicable);
- Known association of the event with the IP, EP or with similar treatments;
- Known association of the event with the disease under study;
- Presence of risk factors in the Study Subject or use of concomitant medications known to increase the occurrence of the event

### 7.1.9 ABNORMAL LABORATORY VALUE

Laboratory abnormalities are usually not recorded as AEs or SAEs. However, laboratory abnormalities (e.g., serum chemistry, CBC, CPK, urinalysis) independent of the underlying medical condition that require medical or surgical intervention or lead to IP interruption or discontinuation must be recorded as an AE, or SAE, if applicable. In addition, laboratory or other abnormal assessments (e.g., electrocardiogram, x-rays, vital signs) that are associated with signs and/or symptoms must be recorded as an AE or SAE if they meet the definition of an AE (or SAE) as described in [Section 7.1](#). If the laboratory abnormality is part of a syndrome, record the syndrome or diagnosis (e.g., anemia) not the laboratory result (e.g., decreased hemoglobin).

Any laboratory abnormality that is new in onset or worsened in severity or frequency from the baseline condition and meets one of the following criteria will be recorded as an AE:

- Requires therapeutic intervention or diagnostic tests
- Leads to discontinuation of study treatment
- Has accompanying or inducing symptoms or signs
- Is judged by the Investigator as clinically significant

### 7.1.10 POST-TRIAL REPORTING REQUIREMENTS

All AEs and SAEs including deaths, regardless of cause or relationship, must be reported for subjects on study (including any protocol-required post-treatment follow-up).

Investigators are not obligated to actively seek AEs or SAEs beyond the follow up period for subjects. However, if the Investigator learns of an AE or SAE that occurs after the completion or termination visit and the event is deemed by the Investigator to be related

to the study treatment, he/she should promptly document and report the event to the study team and medical monitor.

### 7.1.11 PROCEDURES FOR DOCUMENTING PREGNANCY DURING STUDY

Subjects who are pregnant or expect to become pregnant during the course of the study up to 6 months following the last study treatment of investigational product will be excluded from participation in the study. Should a subject become pregnant after enrolling in the study, she will not be given any further study treatments. A Pregnancy Form will be completed by the site personnel and submitted to the sponsor within 24 hours after learning of the pregnancy. Site personnel will submit the Pregnancy Form to the Sponsor as described in [Section 7.4.2](#).

The Investigator will also report this event to the IRB within 24 hours of becoming aware of the pregnancy. Sites must request the subject's permission to query pregnancy outcome and follow each subject to determine the outcome of the pregnancy. Results will be summarized in the clinical study report (CSR).

Subjects who become pregnant at any point during the study will continue to be followed for safety assessments without receiving further study treatment. Procedures that are contraindicated during pregnancy, including additional treatments, must not be performed. Investigators should use clinical judgment regarding subsequent study-related blood collection based on the presence or absence of anemia in each subject. Subjects who are not withdrawn will continue to be followed for safety assessments to study discharge per protocol.

All pregnancies that occur from the time of first study treatment through the follow up visits must be reported. The Investigator will monitor the subject and follow the outcome of the pregnancy. If the end of the pregnancy occurs after the study has been completed, the outcome will be reported directly to the study team and the medical monitor.

## 7.2 METHODS AND TIMING OF COLLECTION OF SAFETY DATA

Non-serious AEs and SAEs will be collected for each subject from the time when informed consent is obtained through Week 100.

The sources of AEs cover:

1. The subject's response to questions about her health (a standard non-leading question such as "How have you been feeling since your last visit?" is asked at each visit).
2. Symptoms spontaneously reported by the subject.
3. Evaluations and examinations where the findings are assessed by the Investigator to be clinically significant changes or abnormalities.
4. Other information relating to the subject's health becoming known to the Investigator (e.g. hospitalization).

All AEs will be reported on the appropriate CRF. Any SAE occurring during the course of the study must be reported to the sponsor within 24 hours of awareness.

### 7.3 SAFETY AND TOXICITY MANAGEMENT

The Medical Monitor will be responsible for the overall safety monitoring of the study.

Safety assessments include the following:

- Incidence of all adverse events classified by system organ class (SOC), preferred term, severity, and relationship to study treatment
- Changes in safety laboratory parameters (e.g., hematology, serum chemistry, and urinalysis)
- Local and systemic injection site review; special attention will be paid to the examination of the injection site. Administration site reactions and the subject's complaints will be documented.

#### 7.3.1 ADVERSE EVENTS OF SPECIAL INTEREST

Adverse events of special interest (AESI) are the adverse events deemed related to VGX-3100 delivered with CELLECTRA™ 2000 that require expedited communication from the site to the Sponsor and meet any of the following criteria:

- Grade 3 or greater persistent administration site erythema, and/or induration recorded  $\geq 2$  hours immediately after Study Treatment
- Grade 4 or greater persistent administration site pain, tenderness recorded  $\geq 2$  hours immediately after Study Treatment
- Grade 3 or greater fever
- Grade 3 or greater systemic symptoms, including generalized pruritus

As per the Toxicity Grade for Healthy Adults. The most severe grade for that particular event is to be documented in the CRFs.

Sites will inform the Sponsor of an AESI within 24 hours via method described in [Section 7.4.2](#), to discuss whether further dosing should continue.

